There is an increasing body of evidence to suggest that the current recommendations are not sufficient to maintain adequate vitamin D status throughout the year. A 2020 individual participant data meta-analysis show that over 30 µg/day is needed to maintain 25OHD concentration >50 nmol/L during winter, in 90% of the adult population (13). Results also showed that very high intakes (92 µg/day) was required to ensure adequate vitamin D status among >97.5% of the population. These results suggest that the current dietary recommendation of 10 µg/day might be insufficient to maintain optimal vitamin D status for many individuals.

The current recommendations for supplemental vitamin D intake at 10 or 20 µg/day for risk groups, is likely too low to achieve the target levels of 25OHD at >50 nmol/L. One µg/day is assumed to raise 25OHD concentration by 1.2 nmol/L. Thereby, for someone with vitamin D deficiency (i.e. 25OHD <30 nmol/L), 15-40 µg/day would be needed to achieve 25OHD >50 nmol/L, depending on the severity of the deficiency.

SPECIFIC SCIENTIFIC AIMS

The double-blind randomized controlled trial (RCT) will include pregnant women with high risk of vitamin D deficiency. Women will be randomized to one of three groups: usual care, or supplementation with either 20 or 40 µg/day vitamin D/day starting in the first trimester. The PREDIN RCT will be conducted within the antenatal care units in Gothenburg with start in 2021. In addition, the investigators aim to evaluate if the overall vitamin D status and vitamin

D intake have increased since the expanded vitamin D fortification program was initiated in year 2020.

The specific aims are to test the hypotheses that:

1. Maternal vitamin D₃ supplementation with 40 µg/day will be more effective than 20 µg/d in achieving vitamin D sufficiency (25OHD ≥50 nmol/l) in pregnant women
2. Maternal vitamin D₃ supplementation (both 20 and 40 µg) during pregnancy will be more effective than usual care in obtaining vitamin D sufficiency (25OHD ≥50 nmol/l) in pregnant women
3. The expanded vitamin D food fortification program has increased the vitamin D status and vitamin D intake of pregnant women in Gothenburg since 2013-2014
4. Vitamin D status and/or vitamin D intake is related to risk of developing complications during pregnancy or delivery

METHODS AND MATERIALS

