The **PREDIN RCT** is a randomized double-blind trial with three parallel arms, providing pregnant women with either usual antenatal care, or a daily pill of 20 or 40 µg/day vitamin D₃ (cholecalciferol), in the first trimester of pregnancy.

Recruitment and allocation

The study will be conducted within the antenatal care in Gothenburg. At a routine visit in early pregnancy, women will receive study information orally and in writing. A signed informed consent is needed to be included as participant in the study. According to clinical praxis, interpreters will be present when needed. In addition, study information will be translated into other languages, e.g. English, Somali and Arabic.

Inclusion criteria for screening for the RCT are age 18-45 years and gestational week <15. Exclusion criteria are multifetal pregnancy, known disorder to the metabolism of vitamin D, calcium or phosphate (e.g. adrenal gland disorders, kidney disease), ongoing treatment with vitamin D of ≥10 µg/day and difficulties understanding the study information.

Included women will be screened for risk of vitamin D deficiency, using a validated screening tool (manuscript under review), and they will be invited to complete the study questionnaires and have blood drawn for later analyses. These data will be used for aim 3 and 4.

Women at high risk of vitamin D deficiency, defined as a screening score ≥15 points, will be randomized to one of the three study arms. Blindness towards both subjects and research staff will be ensured in the two groups receiving vitamin D supplementation. For practical reasons, the group receiving usual care will be open label.

Power for sample size

Power is based on the difference in the primary outcome, proportion of vitamin D sufficiency (25OHD >50 nmol/L) at follow up in the third trimester, between the groups receiving 20 or 40 µg vitamin D per day. Assuming that 50% and 90% achieve vitamin D sufficiency in the respective groups, 17 participants per group is needed. Assuming 50% retention rate, 102 women will be included and randomized to one of the three groups using a computer generated randomization list. To reach the target sample size of 102 women, it is estimated that approximately 500 women will need to be screened. This is based on a 20% prevalence of high risk of vitamin D deficiency according to the screening tool.

Data collection

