At screening, data on socio-demographic factors, ethnicity, dietary intake, eye color, sun exposure, and health status (including use of medications) will be collected using questionnaires. Blood will be drawn and banked for later analysis. Women will be followed up in the third trimester of pregnancy, through assessment of dietary intake and blood draw. Compliance and adverse events will be monitored through questions posed by the midwife in the third trimester at the follow-up visit.

Banked blood will be analyzed for 25OHD and other vitamin D metabolites, nutritional biomarkers, inflammation, hormones and gene variants related to vitamin D metabolism.

[figure not shown]

Figure 1. Study design for the PREDIN study

For all women, information on gestational complications, fetal growth and gestational age at birth will be retrieved from medical records via the antenatal care after birth. Retrieved variables for the child will include weight, length, head circumference, vitality signs (Apgar score), gestational duration, and diagnosis of small-for-gestational age, large for gestational age or intrauterine growth restriction. Data for the pregnant woman will include body weight development, hemoglobin, ferritin, plasma glucose, blood pressure delivery mode and

pregnancy complications (e.g. gestational diabetes, gestational hypertension, and preeclampsia). Analyses of genetic variants relating to D vitamin metabolism will also be analysed.

Analyses of serum 25OHD (25OHD3 and 25OHD2) and vitamin D metabolites (e.g. 3-epi-25-Hydroxyvitamin D3, 1,25-dihydroxyvitamin D [1,25(OH)2D]) and vitamin D binding proteins) in maternal blood will be performed by the golden standard method liquid chromatography tandem-mass spectrometry (LC-MS/MS) in a lab accredited by the vitamin D external quality assessment scheme (DEQAS; <http://www.deqas.org>). Analyses of serum from pregnant women will be performed in batch after the last sample collection. Other analyses of blood includes biomarkers of nutrition status (e.g. nutrients, ferritin, hemoglobin, and metabolomics), inflammation (e.g. CRP, interleukines and cytokines) and bone metabolism, hormones (e.g. cortisol, PTH and sex hormones), as well as gene variants related to vitamin D metabolism.

A total amount of 15 mL blood will be drawn at both screening and follow up. Thus, the total amount of blood drawn will be 30 mL.

Statistical analyses

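### Adverse events outside the record-based pregnancy and birth outcomes, and pill compliance, are asked about only at a visit that half the randomised women are expected not to complete

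*Combined protocol and SAP*

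**What the plan says.** Under Data collection, the only described way of learning about adverse events and compliance is a set of questions at one visit: "Compliance and adverse events will be monitored through questions posed by the midwife in the third trimester at the follow-up visit". Supplementation starts in early pregnancy; screening requires a gestational week below 15. The visible text describes no contact in between, no route for spontaneous reports, no approach to women who miss the visit, and no recording of why a woman stopped.

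Under Power for sample size, the plan expects heavy loss by the third trimester: "Assuming 50% retention rate, 102 women will be included and randomized to one of the three groups".

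A second source does not depend on the visit. Under Data collection: "For all women, information on gestational complications, fetal growth and gestational age at birth will be retrieved from medical records". The variables listed there include pregnancy complications, blood pressure, glucose, haemoglobin, ferritin, mode of delivery, Apgar score and birth size. Tolerability events, pill use and reasons for stopping are not listed.

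Under Statistical analyses, completers form the main analysis. A per-protocol analysis takes women more than 80% compliant, and the three arms are compared on drop-out, compliance and missed visits as a check for bias.

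**The concern.** Two statements that are each unremarkable combine badly. Adverse events and compliance are asked about once, late, and in person, and the plan expects about half the women to be gone by then. A woman who leaves because the pills disagree with her is a plausible non-attender, so whether her event is recorded may depend on the event itself, and possibly on her arm.

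Three things are at stake. First, adverse-event rates by arm would describe only the women who stayed. Second, the compliance part of the between-arm check would have no data on the women who left, and the plan would hold no reasons for their leaving. Third, membership of the per-protocol set could be settled only for women who were asked. For the 25OHD outcome this third loss adds little, because non-attenders have no follow-up sample either. It matters more for record-based outcomes, which exist for women whose compliance is unknown.

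**Working it through.** **The plan's own figure.** Inputs from Power for sample size: "Assuming that 50% and 90% achieve vitamin D sufficiency in the respective groups, 17 participants per group is needed". Alpha and power are not stated; I assume two-sided 0.05 and 80%. With unpooled variance:

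n = (1.960 + 0.842)² × (0.50×0.50 + 0.90×0.10) / 0.40² = 16.7, rounded up to 17 per group.

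Retention: 17 / 0.50 = 34 per group, and 3 × 34 = 102. The stated 102 is reproduced, with equal allocation implied.

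**How many women are asked.** I read retention as completing the third-trimester follow-up, since the primary outcome is measured there.

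- Adverse events: 102 × 0.50 = 51 asked and 51 not asked; 17 and 17 per arm.
- Pill compliance, which concerns only the two supplement arms: 68 × 0.50 = 34 asked and 34 not asked.

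**Precision.** With zero events among n women, the one-sided 95% upper limit is 1 − 0.05^(1/n).

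- n = 17: 16.2%
- n = 34: 8.4%, reached only if information is complete for the whole arm.

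**Bias.** The documents give no adverse-event rate and no attendance by tolerability, so both are assumed. Let q be the true rate, r the attendance of affected women, and 0.50 the overall attendance. The rate among attenders is q × r / 0.50. For q = 10%, 34 × 0.10 = 3.4 women per arm are affected. The attendance of the other women that keeps the total at 50% is (0.50 − q × r) / (1 − q).

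| Attendance of affected women (r) | Attendance of the others | Affected women asked, per arm | Rate among the 17 attenders |
|---|---|---|---|
| 0% | 55.6% | 0 | 0% |
| 25% | 52.8% | 0.85 | 5% |
| 50% | 50.0% | 1.7 | 10% |
| 75% | 47.2% | 2.55 | 15% |

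For q = 5% or 20%, r = 25% gives 2.5% or 10%. The rate is too low when r is below 50%, correct at 50%, and too high above it. If r differs between arms, equal true rates look unequal: 10% in both arms reads as 5% against 10% when r is 25% in one and 50% in the other.

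**Dividing by all randomised women is no cure by itself.** With q = 10%, attendance unrelated to events and non-attenders counted as event-free, the rate is 1.7 / 34 = 5%. That is the same understatement as in the 25% row. The honest bounds with 17 women unknown run from 1.7 / 34 = 5% to (1.7 + 17) / 34 = 55%.

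**The case against.** The strongest reply is that the plan already captures the outcomes that matter most in pregnancy. Complications, blood pressure, glucose, delivery and neonatal outcomes are retrieved from records for every woman, and gestational complications are compared between arms. That stands. A reader might infer that safety as a whole is recorded for only about 51 women; the record retrieval contradicts this.

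A second reply also stands: stopping pills is not the same as missing the visit. A woman who stops but attends is asked and counted, and the 80% compliance cut-off shows that the plan expects some followed women to be poor takers. Drop-outs and missed visits can be counted without interviewing anyone, so only the compliance part of the between-arm check is affected.

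Third, a reader might infer that a dose-related problem will be understated. The documents do not show this. The 50% is a planning allowance with no reason given for the loss, and the table shows that bias can go either way or be absent. Nor would complete data make the trial a sensitive safety study. For assumed true rates of 10% and 20%, the power of a two-arm comparison (normal approximation, two-sided 0.05) is about 13% with 17 per arm and 21% with 34.

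Finally, the design figure is not shown, and contact and consent pages were removed. An interim contact could be described there, so the finding is limited to the visible text. None of these replies supplies tolerability events, pill use or reasons for stopping for women who do not come back.

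**Conclusion.** The point holds in a limited form. By the visible text, adverse events outside the record list and pill compliance are sought only at a visit that about 51 of 102 women are expected not to complete. Women who stop and do not return may go uncounted. If attendance depends on tolerability, adverse-event rates by arm are biased, with direction and size unknown. Compliance is known for about 34 of the 68 women given pills.

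This rests on the plan's 50% allowance being borne out, on equal arms, and on no other reporting route in the parts not shown. The primary outcome and the sample size are unaffected. It still merits an amendment, because the stated collection rule gives worse data than one the sponsor could adopt at little cost.

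**What to change.** - For all randomised women, ask about and record adverse events at withdrawal and at routine antenatal contacts that take place anyway, as well as at the third-trimester visit.
- Add adverse events documented in the medical records to the planned post-birth retrieval.
- In the two supplement arms only, also record pill use and the date and reason for stopping, where obtainable. Nothing in the documents shows that antenatal records hold these items, so asking the woman should be the main route. They do not apply to usual care.
- Report by arm the number randomised, the number with adverse-event information and the number unknown. Give rates among those with information, and add a sensitivity range for the unknowns instead of counting them as event-free.
- State how women of unknown compliance are handled in the per-protocol analysis and in the comparison of compliance between arms.

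The cost is a short amendment, a few form fields and a little extra recording by midwives, with no added visits. Record-based events are less detailed than interview data, and some women will remain unknown.

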Mixed models analyses will be used to investigate the change of vitamin D status over time, adjusting for potential confounders. Also, logistic regression will be performed to investigate the odds of ≥ 50 nmol/l and < 50 nmol/l at follow-up. Interactions for BMI, ethnicity and season will be investigated. First the results including all completers will be evaluated (main analysis), thereafter intention-to-treat analysis will be performed including all randomized participants, and lastly per-protocol analysis will be performed including those $> 80\%$ compliant. Differences in dropouts, compliance and missed visits will be compared between the three arms in order to detect potential bias. Logistic regression analysis will be used to assess differences in dichotomous outcomes (such as gestational complications) between treatment arms, and linear regression analysis for continuous outcome data. The study will be registered at <https://clinicaltrials.gov>.

TIME PLAN

[name] has received funding for the study including from the Swedish state under the agreement between the Swedish government and the county councils, the ALF-agreement (ALFGBG-822451 and LFGBG-932690). Ethical approvals was obtained autumn 2021 (Dnr 2021-03871). Recruitment for the PREDIN RCT will start in winter 2021 and is projected to end by winter 2024. Thereafter, analysis of blood samples will be performed, followed by data handling, statistical analyses and reporting.

REFERENCES

1. Bärebring L, et al. Vitamin D Status during Pregnancy in a Multi-Ethnic Population-Representative Swedish Cohort. *Nutrients*. 2016 Oct 22;8(10).
2. Bärebring L, et al. Preeclampsia and Blood Pressure Trajectory during Pregnancy in Relation to Vitamin D Status. *PLoS One*. 2016;11(3):e0152198.
3. Chen YH, et al. Maternal vitamin D deficiency during pregnancy elevates the risks of small for gestational age and low birth weight infants in Chinese population. *The Journal of clinical endocrinology and metabolism*. 2015 Mar 16;jc20144407.
4. Bärebring L, et al. Trajectory of vitamin D status during pregnancy in relation to neonatal birth size and fetal survival: a prospective cohort study. *BMC pregnancy and childbirth*. 2018 Feb 13;18..
5. Qin LL, et al. Does maternal Vitamin D deficiency increase the risk of preterm birth: A meta-analysis of observational studies. *Nutrients*. 2016;8(5).

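### Pregnancy and birth outcomes are to be retrieved from records for all women, yet the main analysis is of completers and no exception is made for these outcomes

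*Combined protocol and SAP*

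**What the plan says.** All places are in the combined protocol and SAP.

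- **Statistical analyses**, after the mixed model and the logistic regression for 25OHD: "First the results including all completers will be evaluated (main analysis), thereafter intention-to-treat analysis will be performed including all randomized participants". A per-protocol analysis of women more than 80% compliant comes last. Completer is not defined.
- **Statistical analyses**, two sentences later: "Logistic regression analysis will be used to assess differences in dichotomous outcomes (such as gestational complications) between treatment arms", with linear regression for continuous outcomes. No analysis set is named for these comparisons.
- **Data collection**, on the source of the outcomes: "For all women, information on gestational complications, fetal growth and gestational age at birth will be retrieved from medical records". The child's variables include "vitality signs (Apgar score), gestational duration, and diagnosis of small-for-gestational age", together with birth size. The mother's include delivery mode and pregnancy complications.
- **Data collection**, on the only study visit after screening: "Women will be followed up in the third trimester of pregnancy, through assessment of dietary intake and blood draw". No gestational week is given.
- **Power for sample size**: "Assuming 50% retention rate, 102 women will be included and randomized to one of the three groups".
- **Recruitment and allocation**: the two supplement groups are blinded, and usual care is open label.

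**The concern.** A completer analysis is usually defended on the ground that the endpoint is missing in everyone else. That defence is available for 25OHD, which needs the third-trimester blood sample. It is not available for complications, gestational age, birth size, Apgar score or delivery mode, because the plan retrieves these from records whether or not the woman attends.

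As written, the main between-arm result for these outcomes would come from a subset formed after randomisation. Three things are at stake:

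- precision, because the subset is planned to be half the size;
- completeness, because a pregnancy that ends before the visit cannot enter the subset, although gestational duration is itself one of the outcomes;
- the protection of randomisation, because women who know they are in the open-label arm may attend for different reasons from women taking study pills.

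The plan will compare dropout and missed visits between arms. That can reveal a problem but does not remove it. For outcomes taken from records, the problem can be avoided altogether.

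**Working it through.** **1. The plan's own figures.** Inputs from Power for sample size: "Assuming that 50% and 90% achieve vitamin D sufficiency in the respective groups, 17 participants per group is needed", 50% retention, three arms. Significance level and power are not stated; I assume 0.05 two-sided and 80%.

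- Unpooled two-proportion formula: n = (1.960 + 0.842)² × (0.5×0.5 + 0.9×0.1) / 0.4² = 7.849 × 0.34 / 0.16 = 16.7, rounded up to 17 per group.
- Allowing for retention: 17 / 0.5 = 34 per arm, and 34 × 3 = 102.

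Both stated figures reproduce.

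**2. Size of the two candidate sets.** All randomised: 102 women, 34 per arm. Completers at planned retention: 102 × 0.5 = 51 women, 17 per arm. The 34 is an upper limit. Some records may not be retrievable, and a pregnancy loss has no Apgar score or birth weight.

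**3. Precision.** The standard error of a difference between two arms is proportional to √(2/n), so the ratio is √(34/17) = 1.41.

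| Quantity | 17 per arm | 34 per arm |
|---|---|---|
| Difference detectable with 80% power, (1.960 + 0.842) × √(2/n) | 0.96 SD | 0.68 SD |
| 95% half-width, birth weight, SD 500 g (assumed), t × SD × √(2/n) | 2.037 × 171.5 = 349 g | 1.997 × 121.3 = 242 g |
| 95% half-width, risk difference, 5% risk in both arms (assumed) | 14.7 points | 10.4 points |
| Same, 10% risk (assumed) | 20.2 points | 14.3 points |
| Same, 20% risk (assumed) | 26.9 points | 19.0 points |

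The birth-weight half-widths scale with the SD. Over 450 to 550 g they run from 314 to 384 g with 17 per arm, and from 218 to 266 g with 34. The risk-difference rows use 1.96 × √(2p(1−p)/n).

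**4. Births before the visit.** If completer means attending the visit, a birth before it is excluded and a preterm birth after it is kept. The documents give neither the week of the visit nor a preterm risk, so this is an illustration only. Assume a preterm risk p of 5% to 10%, with a share f of 10% to 50% of preterm births falling before the visit.

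- Women affected among 102: from 102 × 0.05 × 0.10 = 0.5 to 102 × 0.10 × 0.50 = 5.1.
- Apparent preterm risk after removing only these women: p(1−f)/(1−pf). With p = 8%, this gives 7.3% at f = 10% and 4.2% at f = 50%.

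Pregnancy losses before the visit would be additional.

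**5. When selection biases the contrast.** Let r(a,y) be the probability of attending in arm a with outcome y (1 = event, 0 = none). The odds among completers in arm a are the true odds × r(a,1)/r(a,0). Hence the completer odds ratio is the true odds ratio × [r(1,1)/r(1,0)] / [r(0,1)/r(0,0)].

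If attendance depends on the outcome alone, the last factor is 1 and the odds ratio is unchanged. It is biased only if the effect of the outcome on attendance differs between arms. The documents give no input for the size of such a difference, so I put no figure on it.

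**The case against.** Several counter-arguments have force.

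- **Intention-to-treat is already planned.** A reader might infer that half of the observed outcomes are dropped. They are not: the same sentence plans an analysis of all randomised women second. The issue is which result is called main. That still matters, because if the two disagree the plan puts the selected set first.
- **The reach of the rule is inferred.** The completers sentence follows the 25OHD analyses and precedes the sentence on complications. Applying it to record-based outcomes is the natural reading but not an explicit one. If the sponsor meant it for 25OHD only, no set is named for the record-based outcomes, and the same clarification is needed.
- **Completer is undefined.** It could mean a woman whose relevant outcome is available, and then little or nothing would be lost. Because of this, and because the visit has no stated week, a reader who infers that early deliveries are removed by design goes too far. Only births or losses before the visit would be excluded, and only under the attendance definition.
- **A lower event rate is not a biased comparison.** If women with complications attend less often, completers will show fewer events. By step 5, that alone leaves the odds ratio from the planned logistic regression unchanged. Bias needs arm and outcome to act together. Open-label usual care makes this possible, but the documents do not show that it will happen.
- **These are not the primary outcome.** Aims 1 and 2 concern 25OHD. Aim 4 is an association question that draws on all screened women. The between-arm birth comparisons are unpowered and remain imprecise even with all randomised women. This limits the importance of the point but does not justify discarding precision that is already available.

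**Conclusion.** The point holds as a correctable weakness in a secondary analysis. The plan names completers as the main set, exempts no outcome, and retrieves pregnancy and birth outcomes for everyone.

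Reading completer as a woman who attended the third-trimester visit, and taking 50% retention as the planning assumption it is, the main comparison of these outcomes would rest on about 17 rather than up to 34 women per arm, with a standard error about 1.4 times larger. It would omit any birth or loss before the visit, which on the assumed inputs above is roughly 0.5 to 5 births among 102 women. It would also be exposed to selection bias whose presence and size cannot be judged from the documents.

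The primary 25OHD comparison and the stated aims are not affected.

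**What to change.** In Statistical analyses:

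1. Define completer, for example by attendance at the third-trimester visit with a 25OHD sample.
2. Limit the completer-first order to outcomes measured at that visit (25OHD).
3. State that record-based outcomes (complications, gestational age, birth size, Apgar score, delivery mode) are compared between arms in all randomised women with retrievable records, as randomised and regardless of attendance. Make this the main analysis, with completers as a sensitivity analysis.
4. Give the denominator for outcomes that a pregnancy loss leaves undefined, such as birth size and Apgar score, and report by arm the number of women whose records could not be retrieved.

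The cost is a few sentences, ideally added before any outcome is examined by arm. It needs no extra visits, data or participants, because retrieval for all women is already planned.

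### Does the absence of a written regression model for aim 4 (vitamin D status or intake and complications) call for a change to the analysis plan?

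*Combined protocol and SAP*

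**What the plan says.** The fourth hypothesis under Specific scientific aims is that "Vitamin D status and/or vitamin D intake is related to risk of developing complications during pregnancy or delivery". Recruitment and allocation describes inviting included women to fill in questionnaires and give blood at screening, and adds: "These data will be used for aim 3 and 4". Data collection supplies the outcomes: "For all women, information on gestational complications, fetal growth and gestational age at birth will be retrieved from medical records".

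Only some of these women enter the trial arms: "Women at high risk of vitamin D deficiency, defined as a screening score ≥15 points, will be randomized to one of the three study arms". Under Power for sample size, "it is estimated that approximately 500 women will need to be screened", and the trial itself is sized as follows: "Assuming 50% retention rate, 102 women will be included and randomized to one of the three groups".

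The Statistical analyses section describes four models:
- a mixed model for change in vitamin D status, with confounder adjustment;
- a logistic model for sufficiency at follow-up;
- a logistic model for other binary outcomes: "Logistic regression analysis will be used to assess differences in dichotomous outcomes (such as gestational complications) between treatment arms";
- a linear model for continuous outcomes.

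BMI, ethnicity and season appear there as interactions to explore, next to the models in which vitamin D status is the outcome.

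**The concern.** In the first two models vitamin D status is the outcome. The third compares randomized arms, and the fourth, in the same sentence, names no vitamin D exposure. So none of the four puts 25OHD or intake on the exposure side with complications as the outcome, although that is what aim 4 tests.

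The arm comparison cannot stand in for it. Women below the screening cut-off have no arm, and assigned arm is a different exposure from measured status or intake. If it were the only complications analysis run, most of the data collected for aim 4 would go unused.

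The trial also treats part of its own cohort. Two of the three arms receive 20 or 40 µg/day, and everyone in those arms was selected for high risk of deficiency. An analysis that related screening status to complications and ignored arm would mix the effect of low status with any effect of the supplement.

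**Working it through.** **1. The plan's own figures.** Inputs from Power for sample size: 50% and 90% sufficient, 17 per group, 50% retention, 20% at high risk. Alpha and power are not stated; I assume two-sided 5% and 80%.
- Unpooled two-proportion formula: (1.960 + 0.842)² × (0.5 × 0.5 + 0.9 × 0.1) / 0.4² = 7.85 × 0.34 / 0.16 = 16.7, so 17 per group.
- 17 / 0.5 = 34 per arm, and 34 × 3 = 102 randomized.
- 102 / 0.20 = 510, against about 500 stated.

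The chain reproduces, and 34 × 3 = 102 implies equal allocation.

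**2. Who is outside the arm comparison.** 500 − 102 = 398, or 398/500 = 79.6%. With 510 screened it is 408, or 80.0%. Both are upper limits, because screened women are only invited to give questionnaires and blood.

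**3. Who is supplemented.** 2 × 34 = 68 women: 68/500 = 13.6% of the cohort and 68/102 = 66.7% of the high-risk group. Of the other 500 − 68 = 432 women, 34 are high-risk (7.9%).

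**4. Is the aim 4 analysis really undetermined?** Set the sections side by side:
- *Exposure:* Recruitment and allocation assigns the screening questionnaires and blood to aim 4. These are collected at screening, ahead of supplementation, so trial supplements cannot alter the exposure.
- *Outcome:* complications from medical records (Data collection).
- *Population:* all included women who give data, since both sources cover them.
- *Model:* logistic regression is already the plan's method for binary outcomes.
- *Supplementation:* arm is assigned by a randomization list and is therefore known for every randomized woman.

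What is not written is the sentence joining these parts, the confounder set, and how arm enters.

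**5. What ignoring arm could do.** Within the high-risk group, arm is randomized and so unrelated to screening 25OHD on average. Across the cohort, supplementation goes with high risk (68 of 68 against 34 of 432), hence probably with low screening 25OHD. If low status raises risk and supplements lower it, ignoring arm pulls the association toward the null; if supplements raise risk, it pushes the association away. If supplements have no effect, there is no bias by this route. These directions depend on low status truly raising risk: under a true null, ignoring arm could create an association. The document gives no supplement effect on complications, so no size follows. It also does not say that arm will be ignored.

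**6. Would analysts have reason to use the whole cohort?** The Introduction gives 25% of women below 50 nmol/L. Assume a 5% complication rate in the reference group, full data on 500 women and a two-sided 5% test. Power for an odds ratio of 2 is then about 45% in the cohort, against 16% for 34 usual-care versus 68 supplemented women. For an odds ratio of 3 it is 85% against 35%. The questions differ, but the cohort is plainly the informative source.

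**The case for a change.** The strongest case for a change is that leaving the exposure open invites a choice made after the data are seen. The follow-up visit also yields blood and dietary data. Entry excludes women with "ongoing treatment with vitamin D of ≥10 µg/day", so on total intake during the trial the supplemented women would sit above the rest: at least 5 + 20 = 25 µg/day, against typically below 10 + 10 = 20 in the others. By screening diet they would be expected near the bottom, if the high-risk group overlaps with the minority groups that the introduction expects to stay low. The definition therefore decides where 68 women fall, and one sentence in the plan would settle it.

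Part of this stands. No model is written, the confounders are not listed, and the handling of arm is not stated. A sentence would be tidy and cheap.

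The rest is weaker. The total-intake contrast concerns an on-treatment exposure that no section assigns to aim 4; the one sentence on the matter points to screening data. The omission is not peculiar to aim 4 either: aim 3, the comparison with 2013-2014, has no explicit model, so the section reads as the analysis plan for the randomized trial. Nor is it a fault of the arm comparison that it leaves out women without an arm; that is a valid randomized analysis of a different question. A fuller specification would have its own limits: at an assumed 5% rate, 500 × 0.05 = 25 events cannot carry a long list of covariates, and 68 × 0.05 = 3.4 events in supplemented women leave little to estimate by arm.

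**Conclusion.** No change follows. The Statistical analyses section does not write out the aim 4 model, and its only stated complications analysis covers about 102 of at most some 500 women. But an analyst who holds the stated hypothesis, the screening data assigned to it, record-based outcomes for all women and the arm assignment would fit the cohort regression, and would be expected to account for the roughly 68 supplemented women. Nothing in the plan tells them to do otherwise, and no stated rule produces a wrong answer.

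This rests on three readings: that the screening data are the intended exposure for aim 4, as Recruitment and allocation says; that allocation is equal, as 34 × 3 = 102 implies; and that about 500 is a ceiling on the women contributing data. Any bias from ignoring arm is hypothetical in direction and cannot be sized from the document. Aim 4 is observational and not primary, and the comparison of 20 with 40 µg/day on third-trimester sufficiency is unaffected.
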